2.1.3 Study method

(1) The trial was reviewed by the Research Ethics Committee of Qilu Hospital of Shandong University. Patients were obtained from the pediatricoutpatient clinic of Qilu Hospital of Shandong University, with written permissionfrom parents or guardians and, where appropriate, consent from the children. Theinvestigators were responsible for design, data collection, analysis, and interpretation. Data were collected by field researchers. and all data were confidential for theduration of the trial; trialists and data analysts could not communicate data with eachother. Eligible healthy children and children with migraine were recruited in the first step and basic information about the children and headache characteristics were obtainedby the site staff, and blood was retained from the study subjects for Elisa assay, respectively.

(2) Method for determination of tryptophan metabolite content:

①Timing of blood collection

In the case group, blood was collected at any time during the first 2-4 hours of themigraine attack; in the inter-migraine attack group, blood was collected at least 24hours before and after the headache-free period. In the healthy control group, bloodwas collected in a quiet state.

②Storage and testing methods

5 ml of elbow venous blood was collected from patients and healthy children inpurple tubes, and the samples were immediately transferred to ice-cold glass tubescontaining a mixture of anticoagulant and protease inhibitor, and centrifuged at 3000rpm for 5 minutes at 4°C. The supernatant was stored at -80°C, and tryptophanmetabolite levels were measured by ELISA, and the case and control groups were compared and analyzed.

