2.1.4 Data analysis

Statistical analysis was performed using SPSS26.0 software analysis, and statisticaldata were tested for normality, and the mean standard deviation ($x + S$) was used formeasurement data that conformed to the normal distribution, and one-way ANOVAwas applied for comparison between the three groups, and t-test for two independentsamples was used for comparison between two groups. The correlation between theplasma levels between migraine attacks and the duration of the disease was analyzedby SPSS26.0 correlation analysis.

(1) After completing the questionnaire survey, the researchers collected data

and analyzed the risk of migraine in children due to the interaction of multiple factors, and used logistic regression to screen the indicators related to the risk of migraine in children due to the interaction of multiple factors, and established an early assessment model of migraine in children to achieve early detection, early diagnosis and early prevention of migraine in children.

(2) Based on the collected medical history, different group analyses were performed, and the plasma levels of tryptophan metabolites in migraine patients were compared with those in healthy controls by t-test; one-way ANOVA was performed on the plasma levels of tryptophan metabolites between different types of migraine; correlation analyses were performed between the frequency, duration, severity and two types of migraine attacks; and logistic regression was performed to screen for possible influences on the risk of migraine in children. Logistic regression was performed to screen the factors that may influence the diagnosis of migraine in children.

(3) To analyze the diagnostic value of tryptophan metabolite and tryptophan metabolite combined diagnosis by ROC curve, and to analyze whether there is any statistical difference between the three diagnostic indexes by independent sample t-test, and to evaluate the diagnostic indexes of tryptophan metabolite and tryptophan metabolite combined diagnosis by diagnostic test, and to evaluate the diagnostic indexes of tryptophan metabolite and tryptophan metabolite combined diagnosis as the possibility and accuracy of specific diagnostic indexes for migraine in children were evaluated.

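### Group comparisons of ELISA values carry no plate term, and the plan does not ensure that attack, inter-attack and control samples share plates

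*SAP*

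**What the plan says.** SAP 2.1.3(2) sets out the handling of the blood in detail: tubes, additives, centrifuge speed, time and temperature. It continues "The supernatant was stored at -80°C" and closes with the assay and the comparison: "tryptophanmetabolite levels were measured by ELISA, and the case and control groups were compared and analyzed". Plates, runs, kit lots and the placing of samples are not mentioned. SAP 2.1.3(1) says only that "blood was retained from the study subjects for Elisa assay, respectively".

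SAP 2.1.4 fixes the tests. For the main contrast, "the plasma levels of tryptophan metabolites in migraine patients were compared with those in healthy controls by t-test". The general rule is "t-test for two independentsamples was used for comparison between two groups", with one-way ANOVA for three groups and again for different types of migraine. Group is the only factor in each of these. The same ELISA values feed the correlations and the ROC analysis.

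**The concern.** ELISA is run in plates, and all samples on a plate share that plate's calibration error. A t-test on the concentrations treats the children as independent and puts every systematic difference between the groups down to group. If controls tend to sit on one plate and attack samples on another, part of the observed difference is calibration, and the test cannot tell the two apart. The same shift moves the AUC, on which the plan means to judge the metabolites as a specific diagnostic index.

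The three kinds of sample are taken in different circumstances: during an attack, between attacks, and in a quiet state. Assaying them in order of arrival or group by group would therefore be easy to do unless the plan rules it out. The samples are frozen, so the layout can be chosen freely before the assay. Afterwards, plates that hold only one group cannot be repaired by any model.

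**Working it through.** The plan states no sample size, SD, assay CV or number of plates, so there is no figure of its own to reproduce. All inputs below are assumptions. SDs are fractions of the mean.

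**Inputs.** Between-child SD σc = 0.35 (σc² = 0.1225). Plate SD σp = 0.05, 0.10 or 0.15. No true difference, two-sided test at 0.05. The ratio R is the true variance of the difference in means divided by the variance that the t-test expects to see. The false-positive rate is approximately P(|T| > t_crit/√R), with T on the t-test's own degrees of freedom.

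**A. Groups on separate plates, one plate each, 40 per group.** R = 1 + 40σp²/σc².
- σp = 0.05: R = 1 + 0.10/0.1225 = 1.82, rate 0.14.
- σp = 0.10: R = 1 + 0.40/0.1225 = 4.27, rate 0.34.
- σp = 0.15: R = 1 + 0.90/0.1225 = 8.35, rate 0.49.

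**B. Separate plates, two plates each, 60 per group (30 per plate).** R = (σc² + 30σp²)/(σc² + (30/59)σp²).
- σp = 0.05: R = 1.60, rate 0.12.
- σp = 0.10: R = 0.4225/0.1276 = 3.31, rate 0.28.
- σp = 0.15: R = 5.95, rate 0.42.

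**C. Two plates, groups split 75/25 and 25/75, 40 per group.** The difference in means picks up half of the difference between the plates, so R = (σc² + 10σp²)/(σc² + 0.385σp²), where 0.385 = 2 × 0.75 × 0.25 × 40/39.
- σp = 0.05: R = 1.19, rate 0.07.
- σp = 0.10: R = 0.2225/0.1264 = 1.76, rate 0.14 (0.13 by simulation).
- σp = 0.15: R = 2.65, rate 0.22.

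The rate rises with group size. At 60 per group, the factor 10 becomes 15 and 0.385 becomes 0.381; at σp = 0.15, R = 3.51 and the rate is 0.29.

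**D. Two plates, groups balanced, 40 per group.** Plate shifts cancel from the difference but stay in the residual variance, so R = σc²/(σc² + 0.513σp²), where 0.513 = 0.5 × 40/39. This is 0.99, 0.96 and 0.91, with rates 0.049, 0.046 and 0.041. The test is slightly conservative. The cost is precision: at σp = 0.12 the variance of a single value is (0.1225 + 0.0144)/0.1225 = 1.12 times what it need be.

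Simulation of 20,000 studies per setting agrees with A to D to within about 0.01.

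**Does a plate term help?** A second simulation used 4,000 studies per setting, σc = 0.30, 40 samples per plate and 40 or 80 children per group, with the same three plate SDs. The unadjusted t-test gave 0.035-0.043 with balanced plates, 0.048-0.055 with random placement, 0.07-0.27 with a 75/25 imbalance and 0.17-0.55 with separate plates. With plate in the model, the rate was about 0.04-0.06 in every layout where plates held both groups. With separate plates, group and plate cannot be told apart, and a plate term does not rescue the comparison.

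**AUC.** In layout A the difference between two plates has SD σp√2. A shift of that size towards higher case values moves the AUC from 0.50 to Φ(σp√2/(σc√2)) = Φ(σp/σc). This is Φ(0.143) = 0.56, Φ(0.286) = 0.61 and Φ(0.429) = 0.67 for the three plate SDs.

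**The case against.** The strongest objection is one of scope. Plate maps, kit lots and run order are commonly left to a protocol or laboratory manual, and none is shown here, so silence about them does not show that the layout is bad. Both groups are recruited in the first step and the plasma is frozen, which is compatible with one mixed run. The worst false-positive rates come from the layout and not from the t-test. This stands as far as it goes, and it limits the point to a conditional one. It does not dispose of it: a laboratory manual could settle the layout, but it would not change the tests that SAP 2.1.4 fixes, and those have no plate term.

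A reader might infer more in three places:

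- **That plate drift does enter the case-control difference.** This needs more than one plate and an uneven spread of groups. The SAP states neither.
- **That the word respectively in "blood was retained from the study subjects for Elisa assay, respectively" means the groups were assayed separately.** It reads at least as naturally as blood being kept from each group of children, and it is no evidence on plate layout.
- **That ignoring plates breaks the t-test in general because samples on a plate are correlated.** With random or balanced placement, the test keeps its level or is slightly conservative.

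Paired samples from one child are not established either. SAP 2.1.3(2) refers to an inter-attack group, and the planned tests are for independent groups.

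**Conclusion.** The concern holds in conditional form. The plan commits to comparisons of ELISA concentrations without a plate term and does not secure a layout under which that would be harmless. With several plates and an uneven spread of groups, a plate shift can pass for a migraine effect. With an even spread, the loss is precision only; with a single plate, the issue does not arise.

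The range is wide because every input is assumed: from no inflation at all with balanced plates to roughly ten times the nominal error rate with one plate per group and a plate CV of 15%. Nothing in the document shows where in that range this study lies. The point is still worth acting on, because all metabolite aims rest on these values and the layout can be corrected only before the assay.

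**What to change.** In SAP 2.1.3(2), add: *Stored samples are allocated at random to plates, with similar proportions of attack, inter-attack and control samples on every plate. If a child gives more than one sample, all of that child's samples go on the same plate.*

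In SAP 2.1.4, add: *If more than one plate is used, metabolite levels are compared with a linear model containing group and plate, and the ROC analysis is stratified by plate or adjusted for it.* The adjustment should not subtract raw plate means: where groups are uneven over plates, that removes part of a true difference between cases and controls.

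If everything fits on one plate, a sentence saying so settles the matter.

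The cost is a randomised plate map and one model term, with no extra blood or procedures. Assays have to wait until samples can be batched, and a few degrees of freedom go to plate.

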2.1.4 Data analysis

Statistical analysis was performed using SPSS26.0 software analysis, and statisticaldata were tested for normality, and the mean standard deviation ($x + S$) was used formeasurement data that conformed to the normal distribution, and one-way ANOVAwas applied for comparison between the three groups, and t-test for two independentsamples was used for comparison between two groups. The correlation between theplasma levels between migraine attacks and the duration of the disease was analyzedby SPSS26.0 correlation analysis.

(1) After completing the questionnaire survey, the researchers collected data

and analyzed the risk of migraine in children due to the interaction of multiple factors, and used logistic regression to screen the indicators related to the risk of migraine in children due to the interaction of multiple factors, and established an early assessment model of migraine in children to achieve early detection, early diagnosis and early prevention of migraine in children.

(2) Based on the collected medical history, different group analyses were performed, and the plasma levels of tryptophan metabolites in migraine patients were compared with those in healthy controls by t-test; one-way ANOVA was performed on the plasma levels of tryptophan metabolites between different types of migraine; correlation analyses were performed between the frequency, duration, severity and two types of migraine attacks; and logistic regression was performed to screen for possible influences on the risk of migraine in children. Logistic regression was performed to screen the factors that may influence the diagnosis of migraine in children.

(3) To analyze the diagnostic value of tryptophan metabolite and tryptophan metabolite combined diagnosis by ROC curve, and to analyze whether there is any statistical difference between the three diagnostic indexes by independent sample t-test, and to evaluate the diagnostic indexes of tryptophan metabolite and tryptophan metabolite combined diagnosis by diagnostic test, and to evaluate the diagnostic indexes of tryptophan metabolite and tryptophan metabolite combined diagnosis as the possibility and accuracy of specific diagnostic indexes for migraine in children were evaluated.

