2.1.2 Data collection

(1) Data sources: questionnaires, outpatient medical records and auxiliary examination results.

(2) Collection methods: questionnaire survey, medical records review, blood collection.

(3) Data composition: Basic personal information, migraine triggering factors, clinical features of headache, medication, past medical history, ancillary examinations, and blood samples were collected from all enrolled headache patients.

① Basic personal information included name, gender, age, height, weight (calculated BMI) cultural level, residence address, and contact information.

② Migraine triggering factors: genetic factors, endocrine (menstruation), diet (cheese, chocolate, puffed food), psychological factors (sleep, anxiety, depression, emotional stress, etc).

③ Clinical characteristics of headache included: whether the patient was in the attack phase or inter-attack phase, the location of the patient's headache, the nature of the headache, the degree of pain (assessed using the visual analog scale VAS Appendix), the duration of the disease (years), the frequency of the headache, the duration of each headache, the time of the last pain, the presence of aura, aura symptoms, concomitant symptoms (photophobia, phonophobia, nausea, vomiting, gastrointestinal

symptoms),exacerbation and remission. The information of each headache, duration of last pain,presence of aura, aura symptoms, concomitant symptoms (photophobia, photophobia.nausca, vomiting, gastrointestinal symptoms), aggravation and relief factors, familyhistory, etc.

④Also record medication use, past medical history, ancillary test results such asroutine blood, liver function, kidney function, lipids, blood glucose, ECG, TCD, headCT,head MRIhead MRA examination,etc.PedMIDAS scale score, migraine treatment efficacy assessment scale, headachediary

⑤5ml of venous blood

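### The attack versus inter-attack comparison takes no account of headache frequency, which affects a child's chance of being sampled in each phase

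*SAP*

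**What the plan says.** SAP 2.1.3, under timing of blood collection, gives three sampling situations. For the case group, "blood was collected at any time during the first 2-4 hours of" an attack. Then, "in the inter-migraine attack group, blood was collected at least 24hours before and after the headache-free period". Healthy controls are sampled at rest. The inter-attack wording is garbled; I read it as a draw with at least 24 headache-free hours on either side.

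SAP 2.1.2 (3) ③ records "whether the patient was in the attack phase or inter-attack phase" as a characteristic of the patient, along with "the frequency of the headache, the duration of each headache, the time of the last pain". Item ⑤ of the same list is a single 5 ml venous sample.

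SAP 2.1.4 opens with one-way ANOVA "applied for comparison between the three groups" and an independent-samples t-test that "was used for comparison between two groups". Neither has a covariate. Item (2) of 2.1.4 then specifies migraine versus control by t-test, and separately states that "one-way ANOVA was performed on the plasma levels of tryptophan metabolites between different types of migraine". Frequency, duration and severity enter only through correlation analyses. Logistic regression is aimed at migraine risk and diagnosis, not at the difference between phases.

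**The concern.** Nothing in the SAP assigns phase. Whether a child contributes an attack or an inter-attack sample follows from the course of that child's disease and the two sampling windows, and both windows depend on attack frequency. More attacks mean more chances to fall inside the attack window and fewer stretches that are headache-free on both sides of a draw. If the two groups are different children, they can differ in usual frequency before any biological effect of the attack.

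The plan itself treats frequency as possibly related to metabolite levels, since it proposes to correlate them. If such a relation exists, a stable difference between frequent and infrequent sufferers could be read as a change during the attack, or could hide one. ANOVA and t-tests without covariates cannot separate the two, although the variable needed to do so is collected.

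**Working it through.** The SAP states no group sizes, SDs, attack frequencies or expected differences, so there is no planned figure to reproduce. What follows shows direction and plausible range only.

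**Inputs from the SAP.** The attack window and the 24-hour margins come from 2.1.3. The tests without covariates come from 2.1.4.

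**Assumed inputs.** A month of 720 hours; attacks at random times; attacks lasting 6 hours; a 48-hour clear span for the inter-attack draw; attack frequency f per month gamma-distributed and capped at 30; no true phase effect; metabolite and frequency correlated at ρ.

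**Chance of each draw.**
- In the attack window (2 hours wide): f × 2/720. The width cancels when group means are compared, so a 4-hour window gives the same group composition.
- Eligible between attacks: exp(−f × 48/720) × (1 − f × 6/720).

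For f = 12 against f = 1:
- Attack window: 0.0333 against 0.0028, a ratio of 12.
- Inter-attack: 0.404 against 0.928, a ratio of 0.44.

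**Mean frequency in each group**, weighting the source population by these chances:

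| Source mean, CV | Attack group | Inter-attack group | Gap in SDs of frequency |
|---|---|---|---|
| 4, 0.5 | 5.00 | 3.72 | 0.64 |
| 4, 0.8 | 6.57 | 3.36 | 1.00 |
| 4, 1.0 | 7.98 | 3.07 | 1.23 |
| 8, 0.5 | 9.99 | 6.95 | 0.76 |
| 8, 0.8 | 12.74 | 5.77 | 1.13 |

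Most of the gap comes from the attack group. In the first row it moves up by 5.00 − 4.00 = 1.00, while the inter-attack group moves down by 4.00 − 3.72 = 0.28.

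**Spurious phase difference** = ρ × gap:
- ρ = 0.1: 0.1 × 0.64 = 0.06 to 0.1 × 1.23 = 0.12 SD.
- ρ = 0.3: 0.3 × 0.64 = 0.19 to 0.3 × 1.23 = 0.37 SD.
- ρ = 0.5: 0.32 to 0.61 SD (from unrounded gaps).
- ρ = 0: zero.

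**False-positive rate**, two-sided 5%, with n per group and spurious difference d: Φ(d/√(2/n) − 1.96) + Φ(−d/√(2/n) − 1.96). At an assumed n = 50, √(2/n) = 0.2. For d = 0.19 (0.192 before rounding), Φ(−1.00) + Φ(−2.92) ≈ 0.16. Over the five rows the rate is 6–9% at ρ = 0.1, 16–45% at ρ = 0.3 and 36–87% at ρ = 0.5.

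**Simpler cross-check.** Suppose half the source has 10 attacks a month and half has 2, and 2 clear days in 30 are needed.
- Share frequent in the attack group: 10/(10 + 2) = 0.83.
- Inter-attack weights: exp(−10 × 2/30) = 0.513 and exp(−2 × 2/30) = 0.875, so the share is 0.513/(0.513 + 0.875) = 0.37.
- If frequent and infrequent children differ by an assumed 0.5 SD at all times, the spurious difference is (0.83 − 0.37) × 0.5 = 0.23 SD.
- With 6 against 2 attacks the shares are 0.75 and 0.43, giving 0.32 × 0.5 = 0.16 SD.

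Both models give the same direction and, at moderate association, a similar size.

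**The case against.** The strongest reply is that the comparison, the way the groups are formed and the size of the bias are all inferred.

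- **The groups are unnamed.** The three groups in 2.1.4 could be the three migraine categories in 2.1.1 (with aura, without aura, chronic), since item (2) also uses ANOVA for migraine types. This stands as an ambiguity. The phase reading is still the better one: 2.1.3 has just set out three sampled groups, and the comparison of types is specified separately.
- **The same child may give both samples.** Section 1.2.1 describes both draws in migraine patients without calling them groups. If every child gives both, selection on frequency between phases disappears, and the fault becomes an independent-samples test on paired data. Separate children is more likely, given the group wording in 2.1.3, the single listed sample and the choice of tests, but it is not settled.
- **The entry rule may be in the protocol.** The SAP does not say that groups are filled by whoever happens to be available in each phase. A reader might infer it from the windows, but quotas, matching or planned visits may be described elsewhere. The silence on entry is therefore not the fault raised here; the unadjusted test is.
- **Random capture is a simplification.** Reaching the clinic during an attack may depend on severity or access as well as frequency. This stands, and adjusting for frequency would not remove it.

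Two stronger readings are also tempting. One is that frequent sufferers fill one group and infrequent sufferers the other; the working shows strong enrichment mainly in the attack group and usually a modest shift in the other. The second is that the phase contrast is the plan's sole evidence on what an attack changes; the stated objectives are pathogenesis in general, early identification and diagnosis, and no attack-phase conclusion is specified.

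**Conclusion.** The concern holds in a conditional form. If the attack and inter-attack groups are different children, the unadjusted tests in 2.1.4 leave the phase contrast open to confounding by headache frequency, because the plan's own windows make eligibility for each draw depend on it. The direction of the selection follows from the windows if attacks and sampling are unrelated in time. The size of any bias does not follow from the document. On the assumptions shown it runs from about 0.06 SD at a metabolite-frequency correlation of 0.1 to about 0.2–0.4 SD at 0.3, and it vanishes if the two are unrelated. A reader should not take these values as estimates for this study, nor conclude that a phase difference, if found, would be spurious. The change is worth making because it costs almost nothing and improves the phase analysis whether the samples are separate or paired.

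**What to change.** In SAP 2.1.4:

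- Name the three groups, and state whether a child may contribute a sample in both phases.
- Estimate the attack versus inter-attack contrast among children with migraine in a linear model for each metabolite, with usual headache frequency as covariate. Age and usual attack duration are optional additions. Draw any attack-phase conclusion from this model and keep the unadjusted comparison as descriptive.
- Where a child gives both samples, use the within-child difference instead of an independent-samples test.
- Do not adjust for VAS recorded at the sampled visit. Pain at that moment is determined by phase, so it could absorb the effect being estimated.

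Frequency, attack duration and age are already collected under 2.1.2 (3) ① and ③, and no further blood is needed. The cost is revised wording, one extra model per metabolite and a few degrees of freedom. Adjustment deals with frequency only; selection through access or care-seeking would remain and should be acknowledged when results are reported.

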2.1 Experimental protocol

2.1.1 Inclusion and exclusion criteria of study subjects

Case group inclusion criteria:(1) Age 4-18 years old, male and female are not limited. (2) Meet the diagnostic criteria of ICHD-3 with aura, without aura, and chronic migraine. (3) Migraine was diagnosed by two or more specialized neurologists. (4) PedMIDAS score > 11 (5) Migraine had never been treated (6) Patients and families gave informed consent to the study purpose, significance, risks, benefits, and informed consent. Source: Department of Pediatrics Outpatient and Inpatient Unit, Oilu Hospital. Shandong University

Inclusion criteria for the control group:(1) Age 6-18 years, male and female. (2) Did not meet the diagnostic criteria of ICHD-3 migraine and other headaches. (3) Physical health allowed their participation in the study. (4) Patients and their families gave informed consent to the study purpose, significance, risks, benefits, and information of the study. Source: Department of Pediatrics Outpatient and Inpatient Unit, Oilu Hospital. Shandong University.

Exclusion criteria:

(1) presence of drug overdose (2) autoimmune diseases (3) neurological diseases other than migraine, intracranial masses (4) congenital or hereditary diseases (5) diabetes, bronchial asthma, cardiovascular diseases, pulmonary diseases (6) other types of primary and secondary headache.

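### The correlation of inter-attack metabolite level with years of disease is not adjusted for age, so any age trend in the metabolite can appear as a disease-duration effect

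*SAP*

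**What the plan says.** - SAP 2.1.4, opening paragraph: the association of plasma "levels between migraine attacks and the duration of the disease was" to be examined by correlation analysis in SPSS. No coefficient, covariate, partial correlation or regression is named.
- SAP 2.1.2, clinical characteristics: the data include "the duration of the disease (years), the frequency of the headache, the duration of each headache". Disease duration (in years) and attack duration are therefore two separate variables.
- SAP 2.1.1, case group: "Age 4-18 years old, male and female are not limited".
- SAP 2.1.2, basic information: "Basic personal information included name, gender, age, height, weight (calculated BMI"). Age is therefore on file for each enrolled patient.
- SAP 2.1.4, item (2): "correlation analyses were performed between the frequency, duration, severity and two types of migraine attacks", again without a covariate.
- SAP 2.1.4, item (2), on multivariable modelling: "logistic regression was performed to screen for possible influences on the risk of migraine in children". The logistic regressions in items (1) and (2) have migraine risk or diagnosis as the outcome.

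**The concern.** Years since onset cannot exceed age, so the possible range of disease duration widens from the youngest to the oldest cases. Where duration does rise with age, a metabolite that changes with growth or puberty will correlate with duration among cases even if length of illness has no effect. A simple correlation cannot tell the two apart. The logistic models do not help, because they model who has migraine and not how the metabolite varies among those who do.

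Section 1.2.1 says the results of these analyses will be combined to explore pathogenesis. A duration association produced by age would enter that interpretation as if it concerned the illness.

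**Working it through.** The SAP gives no sample size, effect size or correlation for this analysis, so there is no figure of its own to reproduce. Every number below is an assumption used to show the range.

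**Step 1. Size of the distortion.** If the metabolite depends (linearly) on age and not on duration, then

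spurious r(metabolite, duration) = r(metabolite, age) × r(age, duration),

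and the partial correlation given age is 0.

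**Step 2. How strongly age and duration correlate.** Age is taken as uniform on 4 to 18 (range from SAP 2.1.1; shape assumed). Duration patterns are assumed:

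| Assumed duration pattern | r(age, duration) |
|---|---|
| Onset uniform from 4 to current age | 0.65 (= 0.5 × √(12/7)) |
| Onset uniform from 3 to current age | 0.616 |
| Onset uniform from 0 to current age | 0.513 |
| Exponential, mean 2 years, capped at age minus 3 | 0.126 |
| Exponential, mean 1 year, same cap | 0.041 |

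The upper bound set by age does not by itself create a strong correlation. It does so only if long histories are common among the older children.

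**Step 3. Chance of a false positive.** By the Fisher z approximation, z = arctanh(r) × √(n − 3), and the two-sided 5% rejection rate is Φ(z − 1.96) + Φ(−z − 1.96). With n = 100 (assumed), √97 = 9.849:

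| r(age, duration) | r(metabolite, age) = 0 | 0.2 | 0.4 |
|---|---|---|---|
| 0.041 | 5% | r = 0.008, 5.1% | r = 0.016, 5.3% |
| 0.126 | 5% | r = 0.025, 5.7% | r = 0.050, 7.9% |
| 0.6 | 5% | r = 0.12, 22% | r = 0.24, 67% |

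Worked for the last cell: arctanh(0.24) = 0.2448; z = 0.2448 × 9.849 = 2.411; Φ(0.451) + Φ(−4.371) = 0.674.

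The inflation shrinks with fewer patients. For r = 0.24 it is 39% at n = 50 and 25% at n = 30.

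**Step 4. Does adjustment remove it?** In 5,000 simulated datasets per sample size (onset uniform from 3 to current age, r(metabolite, age) = 0.3, no duration effect):

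| n | Simple correlation: mean r, rejected | Partial correlation given age: mean r, rejected |
|---|---|---|
| 50 | 0.18, 25% | 0.00, 4.5% |
| 100 | 0.18, 46% | 0.00, 4.7% |

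**Step 5. Cost in precision.** Adding age multiplies the variance of the duration coefficient by about 1/(1 − r²), with r = r(age, duration), before any gain from a smaller residual variance. At r = 0.6 this is 1/0.64 = 1.56, a standard error about 25% larger. At r = 0.13 it is 1/0.983 = 1.02, under 1%.

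**The case against.** The strongest reply is that nothing in the SAP shows the distortion will occur. It needs both an age trend in the metabolite and a material age-duration correlation, and the document states neither. Cases must never have been treated for migraine, which may favour short histories; with durations averaging 1 to 2 years the error rate stays near 5% to 8%. This stands. It limits the size that can be claimed, but the SAP sets no limit on disease duration, so the favourable case cannot be relied on either.

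A reader might infer that an age trend will be reported as a duration effect. The documents do not support that certainty; they support only that it can be, and that the planned analysis could not tell.

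A second reply is that age adjustment does not isolate disease progression. Current age equals age at onset plus duration, so at fixed age a longer duration is the same as an earlier onset. This also stands. It limits how the adjusted result may be read, but it does not make the unadjusted one preferable.

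A reader might extend the argument to the correlations in item (2). Frequency, attack duration and severity are not bounded by age, so this argument does not support adjusting them. Nor does item (2) as a whole omit the metabolites: its t-test and ANOVA clauses name them, and only the correlation clause does not. Finally, this is one exploratory correlation in a plan made up mainly of case-control comparisons, logistic screening and ROC analysis, and the SAP does not say it will be read as progression.

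**Conclusion.** The point holds in a limited form. The correlation of inter-attack metabolite level with years of disease is unadjusted in a sample spanning 4 to 18 years, age is available, and no other planned analysis separates age from duration. An age trend can therefore be mistaken for a duration effect.

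The size is open. For 100 patients and a metabolite-age correlation of 0.2 to 0.4, the nominal 5% error rate ranges from essentially unchanged (5% to 8%, short durations) to as much as 67% (age-duration correlation 0.6, metabolite-age correlation 0.4). It is exactly 5% if the metabolite does not vary with age. The sample size, the correlations and the duration patterns are all assumptions. The change is worth making because it is cheap, not because harm has been shown.

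The wording of item (2) is a minor, separate matter. Its bare term for duration could mean either recorded variable, though its place beside frequency and severity suggests attack duration.

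**What to change.** In the opening paragraph of SAP 2.1.4, replace the simple correlation with a partial correlation of inter-attack metabolite level with disease duration given age, or a regression of metabolite level on disease duration with age as a covariate. State that, at fixed age, the duration result is equally a result for age at onset and is not to be read as pure progression.

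As a wording edit only, say in item (2) that duration means the duration of each headache, if that is intended, and that the correlations are with metabolite level.

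The cost is a few lines of SAP text and no new data. The statistical price is a wider interval where age and duration are strongly correlated, by about 25% at a correlation of 0.6 on the arithmetic above, and hardly any where durations are short.
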